1519 overminus: the Preschool Randot at near score to be used for the outcome classification will
1520 be the one tested *without* wearing prism or overminus. If this measurement shows a decrease
1521 of at least 2 octaves (at least 0.6 log arcsec) from the enrollment measurement, or to nil, to
1522 avoid adding to testing burden and to the complexity of visits, a confirmatory retest *is not*
1523 needed to be considered a surgical failure for this analysis.

~~1524~~

1526 **6.3.2 Exploratory Analyses in Patients with Baseline Angle > 40 to 50 PD**

1527 Additional exploratory analyses will be stratified by IXT type and conducted in a secondary
1528 cohort of patients whose largest angle by PACT at enrollment is > 40 to 50 PD.
1529

1530 The proportion of patients with surgical failure by 3 years will be calculated and will be
1531 compared between treatment groups using the same method as for the primary analysis.
1532

1532

1533 **6.4 Safety Analyses**

1534 Postoperative complications will be tabulated according to treatment group.

1535

1536 **6.5 Additional Tabulations and Analyses**

1537 The following will be tabulated according to treatment group:

- 1538 1. Baseline demographic and clinical characteristics
- 1539 2. Baseline data for study completers vs. non-completers
- 1540 3. Protocol deviations

1541

1542 A flow chart will be constructed that accounts for all subjects. Visit completion rates will be
1543 tabulated according to treatment group for each visit. The percentage of subjects with visits
1544 completed in window, out of window, and missed for each visit will be tabulated.

1545

1546 **6.6 Interim Analysis**

1547 There are no plans to formally assess surgical failure at a timepoint earlier than 3 years because it
1548 is the long-term outcome that is of clinical interest and because the treatment groups are
1549 expected to differ in the timing of surgical failure and in the criteria met for surgical failure.

1550 Patients receiving unilateral lateral rectus recession with medial rectus resection (R&R) are
1551 expected to fail earlier, due primarily to consecutive esotropia (i.e., overcorrection) which cannot
1552 be managed with prism, whereas patients receiving bilateral lateral rectus recessions (BLRrec)
1553 are expected to have better short-term motor outcomes but fail later, due primarily to recurrence
1554 of the intermittent exotropia over the long term. A treatment group comparison of failure

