100 reoperation was completed after surgical failure was met in addition to cases where reoperation
101 occurred without surgical failure having been met (i.e. against protocol).
102

103 The potential for bias in this treatment group comparison is recognized. Once a patient has met
104 the clinical criteria for surgical failure criteria at an interim follow up visit, the decision to
105 reoperate is at the discretion of an unmasked investigator and therefore could be related to
106 treatment group. To assist in assessing for potential bias, the association between treatment
107 group and reoperation in those meeting surgical failure criteria will be evaluated.
108

109 **1.8 Secondary Analysis – 3-Year Exotropia Control and Angle Magnitude**

110 Secondary outcomes of 3-year exotropia control (distance and near) and 3-year angle magnitude
111 by the Prism and Alternate Cover Test (distance and near) will be assessed in all patients who
112 complete the 3-year visit. All 3-year visit data will be analyzed regardless of what treatment(s) a
113 patient has received and regardless of whether the patient has undergone reoperation. These 3-
114 year control and PACT outcomes will be analyzed as continuous variables and compared
115 between treatment groups using analysis of covariance (ANOVA) models that adjust for the
116 corresponding baseline value (e.g. ANCOVA model of 3-year distance control will adjust for
117 baseline distance control).
118

- 119 **Objective #1: Define the cohort of interest**
- 120
- 121 **Objective #2: Compare the cumulative probability of surgical failure BY 3 years between**
- 122 **BLR and R/R treatment groups (primary outcome)**
- 123
- 124 **Objective #3: Compare the binomial proportion of surgical failure AT 3 years between**
- 125 **BLR and R/R treatment groups**
- 126
- 127 **Objective #4: Compare the cumulative probability reoperation by 3 years between BLR**
- 128 **and R/R treatment groups**
- 129
- 130 **Objective #5: Compare 3-year control and PACT values between BLR and R/R treatment**
- 131 **groups**
- 132
- 133
- 134

135 **Datasets Used**

136 **BASELINE** - one-record per baseline exam for all patients enrolled into in IXT1 (regardless of
137 whether randomized) N=277

138 **MASKEDEXAMS** - one-record per IXT1 masked exam (protocol-specified or unspecified) that
139 was at least partially completed IXT1 N=1344

140 **ROSTER** – one-record per randomized patient analysis dataset N=265

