- 450 4. Compare cumulative probability of reoperation by 3 years for each treatment group using
451 two-sided Z-test
- 452 5. Calculate the treatment group difference (and 95% CI) in the cumulative probability of
453 reoperation by 3 years.
454

455 **Technical Plan**

- 456 1. Define the outcome
457
458
459 Reoperation or botulinum toxin treatment at any time during the study, including cases where
460 reoperation was completed after surgical failure was met and cases where reoperation occurred
461 without surgical failure first having been met (i.e. against protocol).

- 462 2. Determine whether patient was reoperated or underwent treatment with botulinum toxin,
463 regardless of whether he/she first met one of the three surgical failure criteria
464 • Use reoperation outcome and time to reoperation variables created for objective #2.
465
- 466 3. Get cumulative probability of reoperation by 3 years for each treatment group – from K-M
- 467 4. Compare cumulative probability of reoperation by 3 years for each treatment group using Z-
468 test
- 469 5. Calculate the treatment group difference (and 95% CI) in the cumulative probability of
470 reoperation by 3 years.
471

472 Repeat steps #8 - #10 for objective #1 using the reoperation outcome and time to reoperation
473 variables.
474

475 **Objective #5: Compare 3-year control and PACT values between BLR and R/R treatment**
476 **groups**

- 477
- 478 1. Define the outcomes
 - 479 2. Define the cohort
 - 480 3. Compare mean 3-year outcomes between treatment groups

481
482 **Technical Plan**

- 483 1. Define outcomes.
- 484 a. PACT size (distance and near)
 - 485 • Code according to size and type
 - 486 ○ Exodeviations will be coded as positive values (same as in database)
 - 487 ○ Esodeviations will be changed to negative values
 - 488
 - 489 b. Exotropia Control (distance and near)
 - 490 ○ For both distance and near, create numeric values for exotropia control where ‘not
 - 491 applicable’ will be assigned a score of 0, the same as the score for a pure phoria.
 - 492 Note that ‘not applicable’ was entered on the form when no exodeviation was present.
 - 493
 - 494

Table #1: Intermittent Exotropia Control Scale Scoring

5	Constant Exotropia
4	Exotropia > 50% of the 30-second period before dissociation
3	Exotropia < 50% of the 30-second period before dissociation
2	No exotropia unless dissociated, recovers in >5 seconds
1	No exotropia unless dissociated, recovers in 1-5 seconds

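### The 3-year PACT outcome is called magnitude but analysed as a signed value, and a control score of 0 mixes aligned with overcorrected children

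*SAP*

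**What the plan says.** Section 1.8 of the 2017 SAP introduces the "Secondary outcomes of 3-year exotropia control (distance and near) and 3-year angle magnitude" by PACT, also at distance and near. All children who complete the 3-year visit are included, reoperated or not. Each outcome is treated as continuous and compared between arms by ANCOVA, adjusted for its baseline value.

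Objective #5, step 1a, calls the variable PACT size. Exodeviations keep a positive sign; for the others, "Esodeviations will be changed to negative values". The 2018 SAP lists the outcome again as 3-year PACT magnitude.

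Step 1b concerns control. An entry of *not applicable*, used when the child had no exodeviation, "will be assigned a score of 0, the same as the score for a pure phoria". That is the best level of the 0 to 5 scale.

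Protocol 6.6 describes how the arms are expected to fail. R&R patients are "expected to fail earlier, due primarily to consecutive esotropia (i.e., overcorrection) which cannot" be managed with prism, and BLRrec patients are expected to fail later, mainly through recurrent exotropia. Under the 4-30-10 amendment (Protocol Change #5), control was added at the masked exams to learn whether one procedure gives better control when the exodeviation persists or comes back.

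**The concern.** A mean of signed deviations measures average alignment, not average size. An arm with some children well exotropic and others well esotropic can have the same mean as an arm in which every child is nearly straight. A reader told that the outcome is magnitude will take a mean closer to zero as smaller deviations, and the analysis cannot show that.

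The control score has a similar problem. For a straight child, 0 is a fair score. For an overcorrected child it is the best possible score on a scale that does not apply, and the arm mean does not separate the two. The amendment asked about control when exodeviation persists or recurs; the coded score mixes that with how often exodeviation is absent, for good or bad reasons.

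The protocol expects the two operations to err in opposite directions, so the coding may act differently in the two arms. What is at stake is the reading of these two secondary outcomes, each at distance and near.

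**Working it through.** The documents give no expected difference, SD, power or result for 3-year PACT or control, so there is no planned figure to reproduce. Every PD value and percentage below is an assumption, except the arm sizes (101 BLR, 96 R/R; 2017 SAP 1.2).

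**1. What each mean measures.** Let p and m be the proportion and mean size of each type of deviation.

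- Signed mean = p_exo × m_exo − p_eso × m_eso
- Absolute mean = p_exo × m_exo + p_eso × m_eso
- Gap between them = 2 × p_eso × m_eso

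The two agree only if no child has an esodeviation. Two children at +12 and −12 PD have signed mean 0 and absolute mean 12.

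**2. Effect on an arm comparison.** Put 80% of both arms at +8 PD. The other 20% are at 0 in the reference arm and at −10 PD in the comparison arm.

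- Signed: 0.8 × 8 = 6.4 against 0.8 × 8 − 0.2 × 10 = 4.4, so the overcorrected arm is 2.0 PD lower.
- Absolute: 6.4 against 0.8 × 8 + 0.2 × 10 = 8.4, so it is 2.0 PD higher.

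In general, if a fraction f has e PD of esodeviation instead of 0, the signed mean falls by f × e and the absolute mean rises by f × e:

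| f | e = 6 PD | e = 10 PD | e = 20 PD |
|---|---|---|---|
| 5% | 0.3 | 0.5 | 1.0 |
| 10% | 0.6 | 1.0 | 2.0 |
| 20% | 1.2 | 2.0 | 4.0 |

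**3. Effect on the test.** Simulation with 4,000 runs and 91 against 86 children (101 and 96 less about 10%). PACT was normal with mean 8 and SD 6 PD in both arms. A fraction f of one arm was then replaced by esodeviations uniform between 6 and 20 PD. A two-sample t-test at 5% stood in for the ANCOVA.

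| f | Signed difference (PD) | Rejected | Absolute difference (PD) | Rejected |
|---|---|---|---|---|
| 0 | −0.01 | 5% | −0.01 | 6% |
| 5% | −1.07 | 17% | +0.22 | 5.5% |
| 10% | −2.09 | 46% | +0.45 | 9% |
| 20% | −4.24 | 93% | +0.89 | 20% |

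When overcorrection is the only difference between arms, the signed analysis can be significant with a lower mean for the overcorrected arm, while the average size of deviation is slightly larger there.

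**4. Control.** If a fraction f of an arm moves from control score c to esodeviation, scored 0, the arm mean falls by f × c. For f = 10% and c = 1 to 3 the fall is 0.1 to 0.3 points. Over f = 5% to 20% it is 0.05 to 0.6 points.

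**The case against.** The case on the other side is substantial.

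- **Signed PACT is a legitimate outcome.** The SAP discloses the coding, speaks of size and type, and heads the objective with PACT values. It never says that a lower mean is better. If an arm mean fell below zero, the sign would reveal overcorrection. This stands: the fault is in the label and in the missing companion summary, not in the signed analysis itself.
- **Overcorrection is examined elsewhere.** Constant esotropia of at least 6 PD counts as failure in the primary outcome and in failure at 3 years. The 2018 SAP compares it by arm as a cause-specific outcome, and its resolution outcome requires esotropia below 6 PD by SPCT. This stands for constant esotropia. It does not cover intermittent esotropia or esophoria of 6 PD or more, which Protocol 6.1.1 classes as indeterminate, or small esodeviations. The 2018 SAP reports esodeviation only alongside nonsurgical treatment or for children who met the esotropia criterion. No 3-year exo/ortho/eso table by arm is planned.
- **Not every esotropic child scores 0 on control.** Under Protocol 2.5, a micro-esotropia by SPCT with an exodeviation by PACT is scored on the exodeviation. This stands and narrows the point.
- **Absolute PACT has its own bias.** It weights exo- and esodeviation equally, while the failure criteria use 10 PD for exotropia and 6 PD for constant esotropia. This stands, so absolute PACT should accompany the signed result.

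A reader might infer that the coding will favour R&R at 3 years. The documents do not support that. Protocol 6.6 concerns the timing and type of failure, not the proportion esodeviated at 3 years. Early overcorrection may have resolved or been reoperated by then, and reoperated children are in the analysis.

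**Conclusion.** The point holds as one of labelling and completeness. The PACT outcome is named as a size but measures average direction and size together, and a control score of 0 combines aligned with overcorrected children. The coding may not be neutral between arms, but its effect cannot be sized because no 3-year esodeviation rate or SD is given. The figures above rest wholly on assumed rates, and for PACT they mislead only a reader who takes nearer zero as smaller.

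A reader might also infer that most of any signed difference would be cancellation. Take an assumed mixture: 60% of each arm at +4 PD; BLR with 37% at +16 and 3% at −10; R/R with 22% at +16 and 18% at −10.

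- Signed means: 2.40 + 5.92 − 0.30 = 8.02 against 2.40 + 3.52 − 1.80 = 4.12, difference 3.90.
- Absolute means: 8.62 against 7.72, difference 0.90.

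The fall from 3.90 to 0.90 is 77%, but it is not the share due to cancellation. Of the 3.90 PD, 0.15 × 16 = 2.40 comes from fewer recurrences and 0.15 × 10 = 1.50 (38%) from negative values. The rest of the fall is the further 1.50 PD that the absolute scale adds against R/R. The mixture has no source in the documents, so no such share should be quoted.

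The primary outcome is not affected. This is a cheap improvement to two secondary outcomes.

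**What to change.** 1. Relabel the signed PACT analysis as mean alignment, in section 1.8, in Objective #5 and in the 2018 list of outcomes.
2. Add absolute 3-year PACT at distance and at near as the magnitude outcome, with the same baseline-adjusted ANCOVA. The baseline covariate does not change, because eligibility requires an exodeviation of at least 10 PD at both distances.
3. Tabulate exodeviation, no deviation and esodeviation at 3 years by arm, at distance and near.
4. Report by arm how many control scores of 0 were *not applicable*, split into aligned and esodeviated.
5. Keep any control summary restricted to children with an exodeviation descriptive, since that subset is defined by a result of treatment.

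The cost is two extra models and one table, from data already collected. No planned analysis is removed. Because absolute PACT treats the two directions alike, it should sit beside the signed result and not replace it.

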**Bilateral Lateral Rectus Recession Versus Unilateral Recession-
Resect for Intermittent Exotropia**

Statistical Analysis Plan / Technical Plan

March 1, 2017

Version 1.1

1 **IXT1 Three-Year Analysis**

2
3 **1.1 Objective**

4 To compare 3-year outcomes between patients treated with bilateral lateral rectus muscle
5 recession (BLR) versus those treated with unilateral lateral rectus recession (R/R)

6
7 **1.2 Cohort of Interest**

8 197 patients with basic-type IXT with largest preoperative exodeviation between 15 and 40 PD
9 by PACT at remote distance, distance, or near (101 in BLR group, 96 in R/R group).

10
11 **1.3 Primary Outcome – Surgical Failure by 3 Years**

12 The primary outcome of surgical failure by 3 years is defined as follows:

13
14 **Failure** = ANY of the following criteria are met at masked exam occurring between 6 months
15 and 3 years after randomization:

- 16 1. **Exotropia** at distance OR near at any time during the exam (i.e., can be constant or
17 intermittent; determined by a cover/uncover test) with a magnitude of atleast 10 PD by
18 SPCT, confirmed by a retest
- 19 2. **Constant esotropia** at distance OR near (determined by at least 3 cover/uncover tests—
20 one must be before any dissociation) with a magnitude of atleast 6 PD by SPCT,
21 confirmed by a retest
- 22 3. Decrease in Preschool Randot near **stereoacuity** atleast 2 octaves (atleast 0.6 log arcsec)
23 (*see Table 3*) from the enrollment measurement, or to nil, confirmed by a retest

24
25 **Table 1: Preschool Randot Stereotest**

Baseline stereoacuity at enrollment, in arcsec	Level needed at follow up visit to meet surgical failure criteria, in arcsec
40"	200" or worse
60"	400" or worse
100"	400" or worse
200"	800" or worse
400"	Nil

26
27 Patients will also be considered a surgical failure for analysis if they undergo **reoperation** or
28 treatment with botulinum toxin at any time during the study.

29
30 **1.4 Primary Analysis**

31 The cumulative proportion of patients meeting criteria for failure by 3 years will be obtained
32 using the Kaplan-Meier method and compared between treatment groups using the Z test. This
33 will allow patients who drop out prior to 3 years to contribute to the estimation of the proportion
34 of surgical failure at 3 years. In this analysis, all patients who meet surgical failure criteria prior
35 to 3 years will be counted as failures at the first visit at which surgical failure criteria are met.

36

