0	No exotropia unless dissociated, recovers in <1 second (phoria)
Not applicable	No exodeviation present

[figure not shown]
[figure not shown]
495
496 For both PACT and control outcomes, use the 3-year visit data for all patients who completed
497 the 3-year visit, regardless of what treatment(s) were received or if the patient had undergone
498 reoperation.

- 499
- 500 2. Limit the analysis to patients who completed the 3-year visit.
 - 501
 - 502 3. Compare mean 3-year outcome between treatment groups using ANCOVA model.

```
503 proc genmod data = roster;  
504 class trtgroup;  
505 model controlnumdi_36 = trtgroup controlnumdi_0;  
506 where comp_36 = 1;  
507 title 'Comparison of 3-year distance control between treatment groups';  
508 run;  
509
```

510 **Datasets used: MASKEDEXAMS, ROSTER**

511 **Version History**

Version Number	Author	Approver	Effective Date	Revision Description
1.0	[name]	[name] 	1-19-17	Original SAP for outcome data included in submitted AAPOS abstract (note that the analyses were specified in the protocol).
1.1	[name]	[name] 	3-1-17	For the purpose of the AAPOS presentation, added section 1.8 on secondary analyses of 3-year exotropia control and 3-year angle magnitude (note that these analyses were specified in the protocol).

512

1
2
3
4
5
6
7
8
9
10
11
12
13
14
15
16
17
18
19
20
21

IXT1 Primary Manuscript on Basic Primary Cohort

Statistical Analysis Plan for Secondary Outcomes Not Covered in Previous Analysis Plans

May 30, 2018

Revision History

VERSION NUMBER		AUTHOR	APPROVER	EFFECTIVE DATE	REVISION DESCRIPTION (INCLUDING SECTIONS REVISED)
SAP	Protocol				
1.0	5.0 6-21-17	[name]	[name]	5/14/18	Initial version
1.1	5.0 6-21-17	[name]	[name]	6/11/18	In the SAS code on line 425 that creates a p value using a z-score, changed to using the absolute value of the z score (instead of the z score itself) to account for situations in which a two-sided test yields a negative z-score.

22 **Important Notes:**

23 The primary analysis and many of the secondary analyses were completed for several abstracts and
24 presentations preceding completion of the primary manuscript. Below is a list of outcomes which are
25 documented in previous analysis plans plus outcomes which are covered herein.

26 **AAPOS Abstract and Presentation 2017**

- 27 • **Surgical failure by 3 years (primary outcome) (reabeled “suboptimal surgical outcome” at 3**
- 28 **years)**

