1.4 Secondary Analysis – 3-Year Stereoacuity

Secondary outcomes of 3-year stereoacuity (distance and near) will be assessed in all patients who complete the 3-year visit. The 3-year visit stereoacuity will be analyzed regardless of what treatment(s) a patient has received and regardless of whether the patient has undergone reoperation. These 3-year stereoacuity outcomes will be analyzed as continuous variables and compared between treatment groups using analysis of covariance (ANOVA) models that adjust for the corresponding baseline stereoacuity.

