430         title'Calculate CIs and P values';
431     run;
432
433     Datasets used: MASKEDEXAMS, ROSTER
```

434 **Objective #3: Compare 3-year stereoacuity between BLR and R/R treatment groups**

- 435 1. Limit the analysis to patients who completed the 3-year visit.
436 2. Define the outcomes as distance stereoacuity and near stereoacuity.
437 3. Create change in stereoacuity between baseline and 3 years.
438 4. Obtain distribution of 3-year stereo and change in 3-year stereo.
439 5. Compare mean 3-year outcomes between treatment groups adjusting for corresponding baseline
440 stereoacuity.

441 **Technical Plan**
442

- 443 1. Limit the analysis to patients who completed the 3-year visit. Use the 3-year visit data for all patients
444 who completed the 3-year visit, regardless of what treatment(s) were received or if the patient had
445 undergone reoperation.
446 2. Define outcomes as distance and near stereoacuity, using existing log scale stereoacuity.
447
448 3. Create change in stereoacuity as the baseline value minus the 3-year value, so positive values =
449 improvement.
450
451 4. Run proc means to obtain distribution of 3-year stereo and change in 3-year stereo.
452
453 5. Compare mean 3-year outcome between treatment groups using ANCOVA model adjusting for
454 corresponding baseline stereoacuity.
455

456 `proc genmod data = roster;`
457 `class trtgroup;`
458 `model stereodi_36 = trtgroup stereodi_0;`
459 `where comp_36 = 1;`
460 `title1'Comparison of 3-year distance stereoacuity between treatment groups';`
461 `run;`
462

463 **Datasets used: ROSTER**
464

465 **Objective #4: Compare complete or near-complete resolution at 3 years between BLR and R/R**
466 **treatment groups**

- 467 1. Define complete or near-complete resolution outcomes:
- 468 • Complete or near-complete resolution at 3 years without regard to previous failure (post hoc)
 - 469 • Complete or near-complete resolution at 3 years with no previous failure (consistent with pre-
 - 470 specified “success” criteria in the protocol).
- 471
- 472 2. Calculate complete or near-complete resolution outcomes using 3-year alignment, 3-year
- 473 stereoacuity, nonsurgical treatment for IXT during the study, reoperation data. In addition,
- 474 suboptimal surgical outcome **by** 3 years will also be used to calculate complete or near-complete
- 475 resolution AT 3 years with no previous failure.
- 476

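### The SAPs name ANCOVA for 3-year control, PACT and stereoacuity but print default PROC GENMOD, whose standard errors and p-values are slightly smaller than those of t-based ANCOVA

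*SAP*

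**What the plan says.** **March 2017 SAP.** Section 1.8 says that 3-year control and PACT angle, each at distance and near, will be compared "between treatment groups using analysis of covariance (ANOVA) models that adjust for the" matching baseline value. Objective #5, Technical Plan step 3, repeats the intention: "Compare mean 3-year outcome between treatment groups using ANCOVA model". The code below it is "proc genmod data = roster", with the statement "model controlnumdi_36 = trtgroup controlnumdi_0". This is the distance-control model. No code is printed for near control or for either PACT outcome.

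**May 2018 SAP.** Section 1.4 says that distance and near stereoacuity will be compared "using analysis of covariance (ANOVA) models that adjust for the corresponding baseline stereoacuity". Objective #3, Technical Plan step 5, again says ANCOVA and prints PROC GENMOD with "model stereodi_36 = trtgroup stereodi_0". No code is printed for near stereoacuity.

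Neither block contains a distribution, link or scale option. Both SAPs carry the instruction "Limit the analysis to patients who completed the 3-year visit", but neither gives the number of completers. The cohort they come from is "197 patients with basic-type IXT with largest preoperative exodeviation between 15 and 40 PD". For these outcomes the steps ask for a comparison of means and do not explicitly list a confidence interval.

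**The concern.** ANCOVA, as the term is normally used, estimates the residual variance as RSS/(n-3) for this three-parameter mean model (intercept, treatment, baseline) and tests the treatment term against a t distribution on n-3 degrees of freedom. PROC GENMOD with no options fits a normal model with identity link, estimates the scale by maximum likelihood (RSS/n) and reports Wald results from the normal or chi-square distribution. Both departures shrink the p-value and any interval, so they add rather than cancel.

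Two things are at stake, both small. A programmer who follows the text in PROC GLM will not get the same standard errors and p-values as one who runs the printed code. And the error rate of these secondary comparisons sits slightly above the level that the named method gives.

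**Working it through.** The documents report no estimate, interval or p-value for control, PACT or stereoacuity, so there is no stated figure to reproduce. The check compares the two procedures directly.

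**Inputs**
- Mean parameters: 3, from the printed model statements.
- Cohort: 197 (March 2017 SAP, section 1.2).
- Completers: not stated. Protocol section 6.7 plans for 10% loss, and 0.9 x 197 is about 177. I show 150 to 197 as the assumed range.
- Rough cross-check on n: the Kaplan-Meier estimates and standard errors printed in the March 2017 SAP (Objective #2, step 10) imply effective numbers p(1-p)/SE^2. These are 0.4594 x 0.5406 / 0.0518^2 = 92.6 and 0.3731 x 0.6269 / 0.0520^2 = 86.5, about 179 in total. This is not a count of completers, but it lies within the range.
- Two-sided 5% level: assumed. The protocol states 0.05 for the primary outcome only.
- GENMOD defaults: standard software behaviour, not stated in either SAP. One run of the code would confirm them.

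**Formulas**
- Ratio of standard errors, GENMOD to ANCOVA: sqrt((n-3)/n)
- Ratio of 95% interval widths: sqrt((n-3)/n) x 1.960 / t(0.975, n-3)
- Type I error of the GENMOD test under normal errors: 2 x P(T on n-3 df > 1.960 x sqrt((n-3)/n))

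**Worked at n = 177.** sqrt(174/177) = 0.9915. The t quantile is 1.9737. Width ratio = 0.9915 x 1.960 / 1.9737 = 0.985, so the interval is 1.54% narrower. GENMOD rejects once the ordinary t statistic exceeds 1.960 x 0.9915 = 1.943, which has two-sided probability 5.36%.

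| n | SE ratio | Interval narrower by | Type I error | GENMOD p when ANCOVA p = 0.050 |
|---|---|---|---|---|
| 150 | 0.9899 | 1.82% | 5.43% | 0.0459 |
| 177 | 0.9915 | 1.54% | 5.36% | 0.0465 |
| 197 | 0.9924 | 1.38% | 5.32% | 0.0469 |

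The type I error column also gives the largest ANCOVA p-value that GENMOD would call significant at 0.05. The window in which a decision changes is therefore 0.050 to about 0.054. At n = 177, an ANCOVA p of 0.055 becomes 0.0514, still not significant.

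**Non-normal outcome.** I simulated a skewed score rounded and clipped to 0-5, with no treatment effect (n = 177, 20,000 runs, distribution assumed). Type I error was 4.8% for t-based ANCOVA and 5.2% for GENMOD.

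**The case against.** The strongest reply is that text and code do not conflict. The SAPs ask for a comparison of means adjusted for baseline, and the GENMOD code fits exactly that mean model with identical point estimates. Nothing in either SAP fixes the variance divisor or the reference distribution, and normal-quantile inference is used elsewhere in the plan: the primary, reoperation and cause-specific comparisons are Z tests with 1.96 x SE limits. The t reference is itself exact only for normal errors, whereas control is a 0-5 score with not-applicable entries set to 0, and near stereoacuity takes a few discrete levels. In the simulation both rates lie within about 1.4 Monte Carlo standard errors of 5% (standard error about 0.15 points).

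Much of this stands. The mean model is right, and the simulation does not show a rate clearly above 5%. What remains is the difference between the two procedures. GENMOD rejects whenever t-based ANCOVA does (1.943 against 1.974 at n = 177), and sometimes when it does not. A reader who sees ANCOVA will expect the t-based result. The Z tests elsewhere are announced as Z tests; these are not.

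A reader might go further and infer that all six secondary comparisons carry materially wrong error bars. The documents do not support that. Code is shown for two of the six, no interval is explicitly planned for any of them, and the shortfall is below 2% over the assumed range. A larger effect would need far fewer patients, for example 2.7% narrower at n = 100, and nothing in the documents suggests an analysis set of about half the cohort.

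**Conclusion.** The point holds as a minor one. For distance control and distance stereoacuity, and by implication PACT, near control and near stereoacuity, the printed procedure gives slightly smaller standard errors and p-values than the ANCOVA that the text names. With 150 to 197 completers, any 95% interval would be about 1.4% to 1.8% too narrow, and type I error about 5.3% to 5.4% under normal errors. Only an ANCOVA p-value between 0.050 and about 0.054 would change sides at 0.05.

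This rests on the assumed number of completers, on GENMOD's default behaviour, and on the same code being used for the outcomes whose code is not printed. Point estimates do not change. The primary Kaplan-Meier comparison, the Fisher and Barnard tests and the Wilcoxon questionnaire tests do not use this code and are unaffected.

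**What to change.** Run the control, PACT and stereoacuity comparisons in PROC GLM: `class trtgroup; model outcome_36 = trtgroup outcome_0; lsmeans trtgroup / pdiff cl;`, with the same restriction to 3-year completers. Report the t-based p-value and interval, and say in both SAPs that the code applies to all six outcomes. The May 2018 SAP already uses PROC GLM with this class and model structure for its questionnaire assumption checks (Objective #5, step 2), so no new method is introduced.

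The edit is about one line per outcome. The real cost is rerunning and re-verifying: the notes at the front of the May 2018 SAP say that the control and PACT outcomes were rerun on post-closeout data in August 2017. If the sponsor prefers not to rerun, the lesser remedy is a sentence stating that maximum-likelihood Wald inference was intended. That removes the mismatch with the text but leaves the slightly smaller p-values.
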